### **6.3.4 Clinical Genotyping Analysis Population**

All healthy volunteers who have provided a sample will be included in the analysis.

## **6.4 SUMMARIES OF TREATMENT GROUP COMPARABILITY**

Descriptive statistics will be generated for demographic and baseline disease characteristics including sex, age, weight, height, body mass index.

For continuous variables, mean, standard deviation, median, and minimum and maximum values will be presented. For categorical data, the proportion of study subjects in each category will be summarized.

## **6.5 SAFETY ANALYSES**

All safety analyses will be based on the safety analysis population.

### **6.5.1 Adverse Events**

The original terms recorded on the eCRF by the Investigator for adverse events will be standardized by the Sponsor.

Adverse events will be summarized by mapped term and appropriate thesaurus level.

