#### **STATISTICAL METHODS**

##### **SAFETY ANALYSES**

All healthy volunteers who have received at least one dose of the study medication, whether prematurely withdrawn from the study or not, will be included in the safety analysis. The safety data, including AEs, reasons for withdrawal from study, laboratory data, ECG, concomitant medications, vital signs, and physical examination results will be listed and summarized descriptively.

As appropriate, listings, summary tables and graphs (subject plot and/or mean plots) will be provided for safety and tolerability assessments.

Adverse events will be listed and summarized by body system and preferred term.

For laboratory data, subject listings will be presented with abnormalities flagged.

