### **3.1.3 Treatment Stopping Rules**

Any serious adverse event (SAE) considered related to study drug will lead to an immediate halt of study drug dosing and enrollment of new subjects until a thorough investigation has been conducted by the Sponsor's Clinical Team and the Principal Investigator. The sponsor or designee will notify all investigators and IRBs/EC regarding the outcome of such investigation, and the study will only continue if agreed by the IRBs/EC.

Planned dose escalation will be stopped if one of the following circumstances occurs in subjects dosed with RO7020531, unless it is apparent that the occurrence is not related to the administration of study medication:

- Within a cohort, three or more subjects on active drug experience:
- Severe and clinically significant (as defined by the Investigator) RO7020531-related AEs of the same character, or
- Clinically significant RO7020531-related laboratory abnormalities of the same character, or
- Clinically significant RO7020531-related changes in vital signs or ECGs of the same character (e.g., confirmation of mean corrected QT interval [QTc] 500 msec or 60 msec longer than the pre-dose baseline).
- Within two consecutive dose cohorts, four occurrences of any of the above conditions in subjects receiving active drug.
- Any other findings (regardless of the incidence rates) that, at the joint discretion of the Sponsor and the Investigator, indicate dose escalation should be halted.
- Dose escalation will not proceed if it is predicted that higher doses of RO7020531 will not result in a further increase in RO7011785 plasma exposure; or if the mean systemic exposure (AUC) reaches the RO7011785 plasma levels found to be associated with dose-limiting toxicities in the global EIH study.

If dose escalation is stopped, lower doses could be investigated by mutual agreement between the Sponsor and the Investigator.

For an individual subject in the MAD cohorts, dose continuation will not occur if the subject experiences any of the following:

- Clinically significant RO7020531-related changes in safety parameters that are considered not acceptable by the Investigator and/or the Sponsor; or
- Poor tolerability, which is considered to affect the subject's well-being and/or the PK evaluation.

Due to the exploratory nature of this clinical study, its conduct can be discontinued at any time at the discretion of the Sponsor.

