## 5.2 SAFETY PLAN

### **5.2.1 Management of Specific Adverse Events**

Flu-like symptoms: TLR7 agonists can be associated with dose-dependent flu-like symptoms. A percentage of healthy volunteers may develop fever, chills, fatigue, myalgia, malaise, and headache within several hours after the dosing with RO7020531. Symptomatic treatment is recommended in case these events occur.

No dose modification of RO7020531/placebo for safety reasons will be implemented in the MAD part of this study. At the discretion of the Investigator, study treatment can be discontinued. For the treatment stopping rules in individual healthy volunteers and dose escalation stopping rules, please see Section 3.1.3 and Section 4.7.1.1.

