#### **5.3.5.1 Diagnosis versus Signs and Symptoms**

A diagnosis (if known) should be recorded on the Adverse Event eCRF rather than individual signs and symptoms (e.g., record only liver failure or hepatitis rather than jaundice, asterixis, and elevated transaminases). However, if a constellation of signs and/or symptoms cannot be medically characterized as a single diagnosis or syndrome at the time of reporting, each individual event should be recorded on the Adverse Event eCRF. If a diagnosis is subsequently established, all previously reported adverse events based on signs and symptoms should be nullified and replaced by one adverse event report based on the single diagnosis, with a starting date that corresponds to the starting date of the first symptom of the eventual diagnosis.

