### **6.1 DETERMINATION OF SAMPLE SIZE**

Four to six cohorts may be evaluated in the SAD part of the study (approximately 40-60 subjects in total), and *two to three* cohorts are anticipated for the MAD part of the study with approximately 20-30 subjects in total.

Ten healthy volunteers are planned to be enrolled at each dose level. They will be randomized to either active treatment (eight healthy volunteers per dose level) or placebo (two healthy volunteers per dose level). With eight healthy volunteers per dose group or cohorts, there is a 90% chance to observe at least one AE that has an incidence rate of 25% in the population.

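### No subject count per dose is planned for the flu-like reaction, the one specific reaction the safety plan expects, and the adverse event recording rule can spread it over several rows

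*Combined protocol and SAP*

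**What the plan says.** Section 5.2.1 is the whole of the plan for specific adverse events, and it covers one reaction: "TLR7 agonists can be associated with dose-dependent flu-like symptoms". It lists six components and their timing: "A percentage of healthy volunteers may develop fever, chills, fatigue, myalgia, malaise, and headache within several hours after the dosing with RO7020531".

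Two places describe how adverse events are analysed. Section 6.5.1: "Adverse events will be summarized by mapped term and appropriate thesaurus level". Synopsis, Safety Analyses: "Adverse events will be listed and summarized by body system and preferred term". Neither names the dictionary. Neither defines a grouped flu-like event, and the reaction appears neither in the events of special interest (section 5.1.3) nor by name in the safety outcome measures (section 3.3.1).

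The recording rule in section 5.3.5.1 begins: "A diagnosis (if known) should be recorded on the Adverse Event eCRF rather than individual signs and symptoms". Separate symptom entries are allowed when the picture cannot be put down to one diagnosis or syndrome at the time of reporting. They are replaced by a single entry if a diagnosis is made later.

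On cohort size, section 6.1 says: "They will be randomized to either active treatment (eight healthy volunteers per dose level) or placebo (two healthy volunteers per dose level". It adds that with eight active subjects "there is a 90% chance to observe at least one AE that has an incidence rate of 25% in the population".

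**The concern.** Two subjects with the same reaction can enter the database differently. One may contribute a single syndrome term; the other may contribute up to six symptom terms. The choice is the investigator's and may vary between subjects and cohorts. A table by term then shows several thin rows, and the reader cannot add them up, because one subject may sit in more than one row.

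With eight active subjects per dose, this matters most for the question the trial is built to answer: how many subjects had the expected reaction at each dose, and does that number rise with dose? As written, the answer would have to be put together from listings after the data are known, by a sponsor team that section 4.3 leaves unblinded.

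**Working it through.** **Inputs from the documents.** Eight active and two placebo subjects per cohort (section 6.1); six components (section 5.2.1); four to six SAD and two to three MAD cohorts (section 6.1); the global study's adverse event experience (section 1.2.2).

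**Assumptions, not in the documents.** Reaction rate 25% to 50%; each affected subject reports k of the six symptoms, chosen at random; no background events unless stated.

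**1. The plan's own figure.** P(at least 1 of 8) at 25% = 1 − 0.75^8 = 0.8999, so the stated 90% reproduces. It applies to one event category that has a 25% rate.

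**2. The same 25% split over rows.** If each affected subject reports exactly one symptom, a given row has rate 0.25/6 = 4.2%, and P(at least 1 of 8) = 1 − (1 − 0.0417)^8 = 29%. If about 80% of affected subjects share each symptom, the row rate is 20% and the figure is 1 − 0.80^8 = 83%. The loss therefore runs from severe to small.

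**3. Visibility in the table.** P(at least 3 of 8) is binomial for the grouped count and simulated (200,000 cohorts of 8) for the largest single row, with all symptoms recorded separately:

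| Reaction rate | Grouped count | k = 1 | k = 2 | k = 3 | k = 4 or more |
|---|---|---|---|---|---|
| 25% | 32% | 2% | 12% | 24% | 32% |
| 40% | 68% | 8% | 36% | 58% | 68% |
| 50% | 86% | 14% | 55% | 77% | 85% |

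Once affected subjects share four or more symptoms, nothing is lost.

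**4. Mixed recording, which section 5.3.5.1 permits.** Suppose the rate is 40% and half the reactions are recorded as a syndrome term. Some row then reaches 3 of 8 in 21% (k = 1) to 39% (k = 4 or more) of cohorts, and in 27% at k = 2, against 68% for the grouped count. High symptom overlap no longer restores the count, because each reaction goes either to the syndrome row or to the symptom rows.

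**5. Low rates.** Section 1.2.2 reports three subjects with related adverse events among 80 dosed in eight single-dose cohorts, one of them at 170 mg. If eight per cohort were on active drug and all three were among them (assumptions), the rates are 3/64 = 4.7% overall and 1/8 = 12.5% at 170 mg. The grouped count then reaches 3 of 8 in only 0.5% and 7% of cohorts. A single row cannot exceed the grouped count, so the difference cannot be larger than that.

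**6. Background.** If each symptom had a 2% to 5% background rate (assumption, independent), the grouped background would be 1 − 0.98^6 = 11% to 1 − 0.95^6 = 26%. With no drug effect it would reach 3 of 8 in 5% to 36% of cohorts.

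**7. Placebo comparison.** Pooled placebo is 2 × 4 = 8 to 2 × 6 = 12 subjects in SAD and 2 × 2 = 4 to 2 × 3 = 6 in MAD. For 0 of 4 the exact 95% upper limit is 1 − 0.025^(1/4) = 60%.

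**The case against.** The strongest reply is that section 5.3.5.1 makes one diagnosis or syndrome the default and separate symptoms the exception, and that section 5.2.1 gives the investigator a name for the syndrome. This stands against a stronger claim that a reader might infer, namely that the reaction will be broken into six terms over several body systems. The documents do not support that claim: splitting is possible, not certain, and the spread over body systems depends on a dictionary they do not name. The thesaurus wording in section 6.5.1 does not exclude grouping either; it only fails to specify it. What survives is inconsistent recording with no regrouping in the analysis, and step 4 shows that mixed recording is itself costly.

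Second, the reaction rates are assumed, and the only data on this drug in the documents show few, mild events. This also stands and limits the size of the point. Multiple-dose rates are not given.

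Third, events are listed by subject in cohorts of ten, and a safety review precedes each escalation (section 3.1.2). Both help while the trial runs. Neither gives a rate by dose for the report.

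A reader might also infer that the stopping rule is undermined. The documents do not support this. Escalation is decided on accumulating data at the review meeting, whereas the tables of complete data follow database lock (section 6). The relevant criterion in section 3.1.3 concerns severe and clinically significant events, while the calculations above count any severity. That section also allows a halt for other findings at any incidence. Its phrase "RO7020531-related AEs of the same character" is undefined, but that is a separate matter of wording.

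**Conclusion.** The point holds as a cheap improvement, not as an error that invalidates the analysis. It rests on the text alone that no subject count by dose is planned for the one specific reaction the safety plan expects, and that the recording rule lets the same reaction appear under different terms.

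The size is a range that rests on assumed reaction rates and symptom patterns. At a 40% reaction rate, the chance of seeing at least 3 of 8 subjects falls from about 68% for a grouped count to between 8% and 68% for the largest single row, and to 21% to 39% with half the reactions recorded as a syndrome. At the related-event rates in section 1.2.2 the difference is negligible. These figures describe what a reader would see in a table; they are not probabilities of stopping escalation.

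**What to change.** In section 6.5.1, before sponsor staff review unblinded data, define a grouped flu-like event:

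- **Terms:** a fixed list made up of the six components in section 5.2.1 plus any single syndrome term. Name the dictionary.
- **Counting:** each subject once, at worst severity, by dose level with pooled placebo, separately for SAD and MAD.
- **Onset:** use the wording of section 5.2.1 or treatment-emergent onset. A fixed 48 h window would have no source in the protocol, and with dosing every 48 h it would cover the whole MAD dosing period and select nothing.
- **Companion count:** a stricter version (syndrome term, or at least two components), so that an isolated headache or fatigue does not drive the result.
- **Components:** keep the individual rows.

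The cost is one definition and one table from data already collected. The grouped rate will include background events, and the placebo group is small (4 to 6 subjects in MAD), so the table is descriptive only.

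Separately, the sponsor should clarify what same character means in section 3.1.3. No clinical rule is proposed here.

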### **6.5.2 Clinical Laboratory Test Results**

All clinical laboratory data will be stored on the database in the units in which they were reported. Healthy volunteers listings and summary statistics at each assessment time

will be presented using the International System of Units (SI units; Système International d'Unités). Laboratory data not reported in SI units will be converted to SI units before processing.

Laboratory test values will be presented by individual listings with flagging of values outside the normal ranges.

#### **6.5.2.1 Standard Reference Ranges and Transformation of Data**

Roche standard reference ranges, rather than the reference ranges of the Investigator, will be used for all parameters. For most parameters, the measured laboratory test result will be assessed directly using the Roche standard reference range. Certain laboratory parameters will be transformed to Roche's standard reference ranges.

A transformation will be performed on certain laboratory tests that lack sufficiently common procedures and have a wide range of Investigator ranges, e.g., enzyme tests that include AST, ALT, and alkaline phosphatase and total bilirubin. Since the standard reference ranges for these parameters have a lower limit of zero, only the upper limits of the ranges will be used in transforming the data.

#### **6.5.2.2 Definition of Laboratory Abnormalities**

For all laboratory parameters included, there exists a Roche predefined standard reference range. Laboratory values falling outside this standard reference range will be labeled "H" for high or "L" for low in healthy volunteer listings of laboratory data.

In addition to the standard reference range, a marked reference range has been predefined by Roche for each laboratory parameter. The marked reference range is broader than the standard reference range. Values falling outside the marked reference range that also represent a defined change from baseline will be considered marked laboratory abnormalities (i.e., potentially clinically relevant). If a baseline value is not available for a healthy volunteer, the midpoint of the standard reference range will be used as the healthy volunteer's baseline value for the purposes of determining marked laboratory abnormalities. Marked laboratory abnormalities will be labeled in the healthy volunteer listings as "HH" for very high or "LL" for very low.

#### **6.5.3 Vital Signs**

Vital signs data will be presented by individual listings with flagging of values outside the normal ranges and flagging of marked abnormalities. In addition, tabular summaries will be used, as appropriate.

#### **6.5.4 ECG Data Analysis**

ECG data will be presented by individual listings with flagging of values outside the normal ranges and flagging of marked abnormalities. In addition, tabular summaries will be used, as appropriate.

Summary descriptive statistics for the actual values and changes from baseline will be tabulated by nominal time for HR, QRS duration, PR and QTcF (see [Appendix 6](#)). For multiple measurements taken at a nominal time-point, the average of these measurements will be used as the value at that nominal time-point in all summaries. In addition, QTcF will be categorized at each time-point as  $\leq 450$  msec,  $>450\text{-}480$  msec,  $>480\text{-}500$  msec and  $>500$  msec and summarized. Similarly, a summary will be provided of the QTcF changes from baseline at each time-point categorized as  $<30$  msec, 30-60 msec, and  $>60$  msec. Changes of the overall ECG interpretation, T-wave and U-wave morphology will be summarized.

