Neither the double prodrug RO7020531, nor its metabolites RO7011785 and RO7018822, significantly affected potassium channels in the *in vitro* human ether-à-go-go-related gene (hERG) assay. Dosing at  $\geq 3\ mg/kg$  in monkeys caused reversible heart rate (HR) increase (with decreased RR interval and shortened QT and/or heart-rate corrected QT [QTc] interval), non-adverse increase in PR interval and increase in body temperature. There were no RO7020531-related effects on respiratory or central nervous system function in rats up to the highest dose tested (300 mg/kg).

No genotoxic potential was observed for RO7020531 in the Ames test, nor in the *in vitro* and *in vivo* micronucleus test. No evidence of teratogenicity or embryo-fetal toxicity was observed in definitive (GLP) embryo-fetal toxicity studies in rats (up to 150 mg/kg/day) or

rabbits (up to 100 mg/kg/day), other than increased incidences of non-adverse fetal skeletal variations. In a definitive (GLP) fertility study in rats, no adverse effects of RO7011785 on mating performance, fertility, or early embryonic development were noted (up to 300 mg/kg, every other day [QOD]), despite slightly reduced body weight gain. See the [RO7020531 Investigator's Brochure](#) for details on the properties of RO7020531 and RO7011785.

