### **3.1 DESCRIPTION OF STUDY**

#### **3.1.1 Overview of Study Design**

For both SAD and MAD parts of the study, each cohort will enroll ten subjects, with eight subjects randomly assigned to RO7020531 and two subjects randomly assigned to placebo ([Table 1](#)). Each cohort will include a minimum of two females, with at least one female receiving active drug. All single and multiple doses will be administered in the fasted state.

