### **3.2.3 Rationale for Pharmacokinetic Assessments**

In general, PK data will be used to describe the concentration-time profile for RO7020531 and its metabolites, as well as key PK characteristics including elimination half-life, dose/exposure and PK/PD relationships for safety and specific TLR7-dependent biomarkers.

For the SAD part of the study, subjects will be asked to remain in the unit for up to 3 days post-dose for safety monitoring and to collect plasma samples for PK. With the proposed collection of up to 48 hours post-dose, it is assumed that the full concentration-time profile for RO7020531 and its metabolites will be determined. Urine samples will be collected in intervals to determine the fraction of RO7020531 and its metabolites that are eliminated in the urine. Previous work with the TLR7 agonist RO6864018 has shown extensive elimination of the active TLR7 agonist RO6871765 in the urine. As both RO7020531 and RO6864018 are from the same chemical class, it is expected that extensive renal elimination of the active TLR7 agonist RO7011785 will occur. It is anticipated that the 24-hour urine collection will allow characterization of this elimination pathway.

For the MAD part of the study, a QOD dosing schedule will be used, and extensive PK sampling will be made over a 24-hour period on Day 1 following the first dose and on Day 13 following multiple doses to determine if PK parameters change with multiple doses. With subsequent doses throughout the dosing period, sparse PK sampling will

also be used to characterize trough values and  $C_{max}$  values to determine that exposure of RO7011785 is maintained during this dose regimen. No urine samples will be collected in the MAD part of the study.

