#### **4.3 METHOD OF TREATMENT ASSIGNMENT AND BLINDING**

This study is observer-blinded. This means that the subjects, the Investigator, and all individuals in direct contact with the subjects at the investigative site will be blinded, except for the pharmacy staff handling the study drug distribution.

This study is Sponsor-open; members of the Sponsor's project and study teams who do not have direct contact with the subjects will be unblinded. This may exclude contract research organization (CRO) staff in direct contact with the site.

Healthy volunteers will be randomized 4:1 to RO7020531 or to placebo in each dose cohort. The randomization numbers will be generated by the Sponsor or its designee. The randomized treatment assignment will be allocated from the list sequentially to subjects in the order in which they are randomized. A minimum of two females per cohort will be randomized, with at least one female receiving active drug. The treatment allocation will be managed by the unblinded site pharmacist(s) and will be based on the randomization code list.

To allow informed recommendations or decisions regarding the dose decisions in this study, an integrated assessment of the available data on PK, select PD, safety and tolerability will be made prior to each dose decision.

In exceptional cases, (e.g., if deemed important for dose decisions or for the more thorough evaluation of safety-related concerns that may impact dosing of future subjects on this or other currently conducted or shortly to start studies involving administration of RO7020531) and in the interest of the subjects' safety, the Investigator may be unblinded after approval by the Clinical Pharmacologist.

The Principal Investigator(s) will receive a set of sealed treatment codes. These may have the form of sealed envelopes or scratch codes. If the identity of the test medication needs to be known in order to manage the healthy volunteer's condition, the treatment code for that healthy volunteer may be broken.

As per Health Authority reporting requirements, the Sponsor will break the treatment code for all unexpected serious adverse events (see Section 5.1) that are considered by the Investigator to be related to study drug.

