## Appendix 2 Schedule of Assessments: SAD Detailed (cont.)

- a) Vital signs include blood pressure, pulse rate, respiratory rate and body temperature. Blood pressure, respiratory rate and pulse rate will be obtained after the subject has been in a supine *or sitting* position for at least 5 minutes. Blood pressure measurement will be performed in triplicate (can be as short as 20-second to 1-minute interval between measurements). Pulse rate and body temperature measurement will be performed as single assessments.
- b) 12-lead ECGs will be obtained in triplicate (three consecutive interpretable 12-lead ECGs within a 2-5 minute interval) after the subject has been in a supine position for at least 10 minutes. Automated ECG intervals (PR (PQ), QRS, QT, QTcF) and HR will be captured or calculated, and the changes in T-wave and U-wave morphology will be documented.
- c) Plasma PK samples will be collected pre-dose and 0.25, 0.5, 1, 1.5, 2, 3, 4, 6, 8, 12, 18, 24, 36, and 48 hours post-dose.
- d) A single void urine sample will be collected pre-dose on Day 1. Pooled urine PK samples will be collected 0 to 4 hours, 4 to 8 hours, 8 to 12 hours and 12 to 24 hours post-dose.
- e) PD samples will be collected at pre-dose, 2, 6, 12, 24, 48 and 96 hours post-dose and follow up visit. Samples at 48 and 96 hours post-dose will be collected for neopterin only (no other PD markers).
- f) If the clinical genotyping blood sample is not collected at Day 1, it may be collected at any time during the conduct of the clinical study.
- g) Study drug will be administered in fasted state (after an overnight fast of at least 10 hours).
- h) A follow up visit to be completed 7 days ( $\pm 1$ ) after the last dose of study medication.

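### The ECG analysis has no placebo contrast and no committed link to exposure, although Section 3.2.3 gives safety as a use of the PK data and the SAD design supports both

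*Combined protocol and SAP*

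**What the plan says.** **Purpose of the PK data.** Section 3.2.3 says they will be used to describe, among other things, "dose/exposure and PK/PD relationships for safety and specific TLR7-dependent biomarkers".

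**ECG analysis.** Section 6.5.4 plans "Summary descriptive statistics for the actual values and changes from baseline will be tabulated by nominal time for HR, QRS duration, PR and QTcF". It adds listings with flags, QTcF grouped by absolute value, and "a summary will be provided of the QTcF changes from baseline at each time-point", grouped as below 30, 30 to 60 and above 60 msec. It does not mention placebo, concentration or pooling, and does not say how the tables are grouped by treatment.

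**Other analysis sections.** Section 6.6 allows further PK and PD analyses, and pooling of data, at discretion; it does not name ECG. Section 6.7 commits to regression relating dosing regimen, PK and PD, in a section whose endpoints are cytokines, chemokines, neopterin and interferon-response genes.

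**Design.** Each cohort has "eight subjects randomly assigned to RO7020531 and two subjects randomly assigned to placebo" (Section 3.1.1), and Section 4.3 confirms that "Healthy volunteers will be randomized 4:1 to RO7020531 or to placebo in each dose cohort". Section 6.1 states: "Four to six cohorts may be evaluated in the SAD part of the study (approximately 40-60 subjects in total").

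**Sampling.** Appendix 2: "Plasma PK samples will be collected pre-dose and 0.25, 0.5, 1, 1.5, 2, 3, 4, 6, 8, 12, 18, 24, 36, and 48 hours" post-dose.

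**Background.** Section 1.2.1 reports that dosing at 3 mg/kg or more in monkeys "caused reversible heart rate (HR) increase (with decreased RR interval and shortened QT and/or heart-rate corrected QT [QTc] interval"), with a PR increase judged non-adverse and a rise in body temperature. It also reports no significant effect in the hERG assay. Section 1.2.2 reports no clinically significant ECG changes or trends in NP39305 at single doses up to 170 mg.

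**The concern.** Safety is the primary objective and ECG abnormality is a listed safety outcome. Section 6.7 delivers the biomarker half of the purpose stated in Section 3.2.3. The safety half has no committed analysis, at least for ECG.

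Two features weaken the planned summaries.

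- **Confounding.** Lunch is given about 4 hours after dosing and an ECG follows at 6 hours. A within-group change from baseline at 6 hours contains the meal and the time of day as well as any drug effect. Placebo subjects on the same schedule carry that shared component, so subtracting their change removes it.
- **Direction.** The QTcF change categories grade prolongation only: a fall of any size lands in the group below 30 msec. The absolute categories likewise have no low band. Shortening, the direction seen in monkeys, would appear only in the by-time means, which have no control beside them, or in individual flags.

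At stake is whether the study can give an interpretable estimate, with an interval, of the effect on HR, PR and QTcF. The data for it are already being collected.

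**Working it through.** **1. The plan's own figure.** The only sample-size figure is the 90% chance of seeing at least one AE of 25% incidence among 8 subjects: 1 − 0.75^8 = 0.8999. It reproduces. It concerns AE detection and says nothing about ECG precision.

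**2. Pairing of ECG and PK in SAD (Appendices 1 and 2).**

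- ECG times: screening, Day −1, pre-dose, 0.5, 1, 2, 4, 6, 12, 24 and 48 h, and Day 8, which makes 12.
- With a PK sample at the same nominal time: pre-dose through 48 h, which makes 9.
- Without one: screening, Day −1 and Day 8.

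**3. Precision of a placebo-corrected change at one dose and one time.** For 8 active and m placebo subjects with a common SD:

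half-width of 90% CI = t(0.95; 6 + m) × SD × √(1/8 + 1/m)

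The documents give no SD for change in QTcF. I assume 8 msec, with a range of 6 to 12 msec.

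| Placebo subjects | t × √(1/8 + 1/m) | In SD units | SD 8 msec | SD 6 to 12 msec |
|---|---|---|---|---|
| 2 (own cohort) | 1.860 × 0.791 | 1.47 | 11.8 | 8.8 to 17.6 |
| 6 (three cohorts pooled) | 1.782 × 0.540 | 0.96 | 7.7 | 5.8 to 11.6 |
| 8 (four cohorts pooled) | 1.761 × 0.500 | 0.88 | 7.0 | 5.3 to 10.6 |
| 12 (six cohorts pooled) | 1.734 × 0.456 | 0.79 | 6.3 | 4.7 to 9.5 |

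The three-cohort row is included because Table 1 marks the 170 mg cohort as optional. With four cohorts, pooling cuts the half-width by (1.47 − 0.88)/1.47 = 40%. These are pointwise intervals, not adjusted for the number of times, doses or parameters.

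**4. What a concentration model might add.** An illustrative mixed model has 32 active and 8 placebo subjects, 8 post-dose times, time effects, a treatment term, a concentration slope and a random subject intercept. It gives a half-width of about 0.50 to 0.62 SD at the mean 170 mg Cmax. This assumes a human half-life of 1.5 to 4 h (the documents give only 1.51 h in rats and 2.12 h in monkeys), within-subject correlation of 0.3 to 0.7, exposure CV of 30%, and an effect that follows concentration without delay. From 1.47 SD the total gain is 0.85 to 0.97 SD, of which pooling placebo alone supplies 0.59 SD, or 61% to 69%.

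**5. What happens if the effect is delayed.** Take a half-life of 2 h, SD of 8 msec and a true peak effect of 10 msec in a simulation. With no delay the model recovers 10.0 msec. If the effect peaks at 5.6 h, it predicts about 3.4 msec at Cmax, and its 90% CI covers the true peak in only about 22% of trials.

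**The case against.** The strongest case on the other side has five parts.

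- **Nothing is forbidden.** Section 6.6 leaves an exposure-ECG analysis open, and Section 3.2.3 is a general rationale that says safety, not ECG. This stands as far as it goes. A reader might infer a broken promise of ECG modelling; the text supports only a stated purpose with no committed analysis behind it.
- **No ECG effect estimate is defined.** A reader might infer that the planned estimate compares 8 subjects with 2. The plan defines no such estimate and does not confine placebo to its own cohort. The 8-versus-2 row is what a reader could derive from one cohort's data.
- **The signal is weak.** A reader might take the monkey findings as a known cardiac risk. The documents do not support that: hERG was not significantly affected, the PR change was called non-adverse, and NP39305 reported no clinically significant ECG changes or trends up to this study's planned maximum dose. That is reassuring, but it gives no effect estimate with an interval.
- **Meal and clock time are partly controlled.** Section 4.6.1.4 asks for conditions close to those pre-dose, including food intake, and footnotes to Appendices 1 and 3 mention time-matched ECGs on Day −1. However, Appendix 2 shows a single untimed Day −1 ECG, lunch still precedes the 6 h recording, and Section 6.5.4 does not define baseline.
- **A direct-effect model may not fit.** Section 3.2.1 expects biomarker activity peaking as late as 48 hours after dosing. This objection stands, and step 5 shows its force. It bears on the concentration model, not on the placebo-corrected change by time.

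Escalation under Sections 3.1.2 and 3.1.3 rests on individual findings and judgement, so no dosing decision in the plan turns on a mean ECG interval.

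**Conclusion.** The gap is real and modest. The plan gives safety as a use of the PK data, yet plans neither a placebo contrast for ECG nor a committed exposure-ECG analysis, although randomised placebo and nine paired SAD times are available.

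The firm gain comes from the placebo-corrected change with pooled placebo: 0.88 SD with four cohorts and 0.79 SD with six, against 1.47 SD within one cohort. In SD units these follow from the documented design, given a common SD and comparable placebo responses across cohorts. The msec figures also need the assumed SD.

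Two stronger readings should be avoided. Not every SAD ECG has a PK sample: 9 of 12 times do. Nor should the concentration model be presented as the main answer, because its further narrowing depends on assumed PK, correlation and a direct effect, and with a delayed effect its tight interval could reassure falsely.

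**What to change.** Add to Section 6.5.4:

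1. For HR, PR and QTcF, the placebo-corrected change from baseline by dose and nominal time, with 90% CI and placebo pooled across SAD cohorts. Define the baseline. Show placebo change by cohort beside it, so that the pooling assumption can be judged. Because this estimate is signed, it shows shortening as well as prolongation.
2. As a secondary exploratory analysis, a linear mixed model of change in each parameter on RO7011785 concentration, with treatment, nominal time and baseline as fixed effects and a random subject effect. Plot mean concentration and mean placebo-corrected change over time first. Interpret the model only if there is no material delay; otherwise the by-time estimates in item 1 stand. State the direct-effect assumption with the results.

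If the sponsor does not want an exposure-ECG analysis, Section 3.2.3 should be narrowed to match; item 1 is worth having either way.

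**Cost:** analysis text and a little programming, with no new samples or visits. Pooling assumes comparable placebo responses across cohorts dosed at different times.
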